+ extended family: a family that extends beyond the nuclear family, including grandparents, aunts, uncles, and other relatives, who all live nearby or in one household.

Patient recruitment and management

The households will be classified into nuclear family type and extended family type. The "Nuclear family type" is defined as husband and wife with baby (aged less than 5 months) and with or without children (2-5) and the "Extended family type" (three-generation family) is defined as husband and wife with baby (aged less than 5 months), children (2-5), and grandparents aged > 65 years old. The exclusion criteria are co-morbid medical conditions of the baby such as chronic lung disease, cyanotic congenital heart disease, neuromuscular disease and a primary immunodeficiency. We will initially complete an enrollment form to collect baseline data, including patient demographics, prior medical history, season when discharge, neonatal course and households. A LINE-based management will be done weekly by study team to see if there are any respiratory symptoms in household. In addition to the monthly physician weekly LINE response, the research nurse will contact the parents or legal guardians by telephone monthly for the 24 months to obtain data on changes in baseline information, and specific facts regarding possible respiratory infections after the last contact.

Study endpoint

The primary endpoint is the *S. pneumoniae* and RSV isolation rates in children and their household contacts of different family type. The secondary endpoint is the serotype of *S. pneumoniae* and RSV in post-PCV13 era.

Study design

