Households with at least 1 ARI case during the study period will be included for data analysis. A household with ARI in different years will be treated as 2 different households. Because household visits will be conducted weekly, we will collect specimens for ARI episodes as possible. We will identify these ARI through symptom records. The ARI cases in RSV or *S. pneumoniae* whose dates of onset are within 10 days before or after RSV or *S. pneumoniae* onset will be identified and defined as preceding and subsequent ARI, respectively. We will apply a Bayesian approach to estimate acquisition and clearance rates for RSV or *S. pneumoniae* in a susceptible-infected-susceptible model [37]. The inference relies on repeated measurements of the current status of being a non-carrier (susceptible) or a carrier (infected) of one of the pathogens. We will collect the measurements with sampling intervals. The index cases are the first members of the household to have clinically apparent illness confirmed by laboratory studies. The secondary cases are defined as other family members whose respiratory symptoms occurred later than the index cases' illness. Identified source of infection within the household is defined as the first case in the household who displayed clinically apparent disease and who have clear contact history with individuals outside the household who had illnesses suggestive of *S. pneumoniae* or RSV infection. The infection transmission interval will be defined as the time between the onset of disease for the first case in the household and the onset of disease in a secondary case [38].

Hierarchical generalized linear mixed effect models (HGLMEM)

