In order to assess variables that are significantly impacted in *S. pneumoniae* or RSV infection status across time points in 2 different households, we will fit several random and fixed effects three-level longitudinal generalized hierarchical linear mixed effect models (HGLMEM) with restricted maximum likelihood (REML) estimation method [39, 40]. HGLMEM will be used to evaluate longitudinal *S. pneumoniae* or RSV infection status measurement across time points (level 1) that are nested-within individual subject (level 2) and nested-within household (level 3). Because the model can assume random time effects of measurement, HGLMEM will be a practical strategy for analyzing our data sets. Random effects account for within-subject correlation and will be fitted an unstructured (UN) covariance structure. The structure implies that all different members of a cluster are differently correlated with each other across time. Fixed effects such as the clinical covariates (including clinical data, candidate markers, and target genes), baseline assessment in *S. pneumoniae* or RSV infection status, and household group \times time interaction term will be all included to reflect differential patterns of change over time for the two different household groups. Different fixed effects covariates' combination hierarchical models will be built in the three-level HGLMEM. The HGLMEM will be used to compare the change of *S. pneumoniae* or RSV infection status across time points and to survey the potential associations between these outcomes and independent variables.

Data will be summarized using descriptive statistics. Continuous variables will be expressed as median with interquartile range (IQR) and compared using Mann-Whitney U test. Categorical variables will be presented as frequency and percentage and compared using chi-square or Fisher's exact test, as appropriate. A *P* value less than 0.05 will be considered statistically significant.

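### REML is named for a three-level mixed model of a two-state infection outcome; run in its usual form, linearised pseudo-likelihood, it would understate the family-type odds ratio and the variance components.

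*Combined protocol and SAP*

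**What the plan says.** Under Statistical Methods, the HGLMEM section of the combined protocol and SAP plans several generalized hierarchical mixed models of infection status "with restricted maximum likelihood (REML) estimation method". Time points are "nested-within individual subject (level 2) and nested-within household (level 3"). The random effects have an unstructured covariance and may include time. Fixed effects include clinical covariates, baseline status and a household group by time interaction. The section adds: "Different fixed effects covariates' combination hierarchical models will be built in the three-level HGLMEM".

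The section does not give the outcome distribution, the link, the way the random effects are integrated out, or the software for these models. The nature of the outcome has to be taken from the Infected model section, which speaks of the "current status of being a non-carrier (susceptible) or a carrier (infected) of one of the pathogens".

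Two other statements fix the amount of data per cluster:

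- **Household size** (Patient recruitment and management). A nuclear family is "husband and wife with baby (aged less than 5 months) and with or without children (2-5"). An extended family has the couple, the baby, "children (2-5), and grandparents aged > 65 years old".
- **Samples per person** (Infected model). No number is given, only that "we will collect specimens for ARI episodes as possible".

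**The concern.** REML corrects the variance estimates of a Gaussian linear mixed model for the fixed effects that were fitted. A mixed model for a two-state outcome has no closed-form likelihood, so the integral over the random effects must be approximated. Naming REML does not say how. The usual way to run it on binary data is restricted pseudo-likelihood: linearise the model around the current fit, treat the working response as Gaussian, apply REML and iterate. That linearisation is poor for binary data with few observations per person and few people per household, which is this design.

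The size of the difference between nuclear and extended families is at stake, together with the person and household variation. The primary endpoint is isolation rates by family type, so the magnitude of that contrast matters as well as its P value.

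A second, smaller issue follows from the same word. Models with different fixed effects are planned, and REML or pseudo-likelihood values cannot be compared across them.

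**Working it through.** **1. Inputs from the document.** Power/Sample Size gives 29-46% for nuclear and 38-50% for extended families, 80% power, a 5% level, 93 per group, and 120 households per group with 15% loss. Evaluable households: 120 × 0.85 = 102 per group.

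**2. The plan's own figure.** With 29% vs 50%, two-sided:

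- n = [1.960·√(2·0.395·0.605) + 0.842·√(0.29·0.71 + 0.50·0.50)]² / 0.21² = 83.9, so 84 without continuity correction.
- With the correction: (83.9/4)·[1 + √(1 + 4/(83.9·0.21))]² = 93.2, so 94 rounding up, against the stated 93.
- Allowing for loss: 93/0.85 = 109.4, so 110, which 120 covers.

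The 93 is reproduced and does not depend on REML. The same pair sets the true effect below: OR = (0.50/0.50)/(0.29/0.71) = 2.45, log OR = 0.895.

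**3. Assumptions, not in the document.** Random-effect SDs on the logit scale; 2, 3 or 8 measurements per person; households of 3-4 (nuclear) and 6 (extended: one child, two grandparents).

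**4. Model and fits.** For time t, person i, household j:

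logit P(y = 1) = β₀ + β₁·extended + u_j + v_ij, with u ~ N(0, σ_h²) and v ~ N(0, σ_p²).

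- *Quadrature ML* integrates u and v numerically (21 points per level).
- *PQL-REML* replaces y by z = η̂ + (y − p̂)/[p̂(1 − p̂)], with weights p̂(1 − p̂), fits a linear mixed model by REML, and iterates.

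**5. Results.** 102 households per group, 120 replicates, true log OR 0.895; Monte Carlo SE of the PQL mean 0.010-0.015:

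| σ_h = σ_p | Measurements | ML log OR (OR) | PQL log OR (OR) | PQL shortfall | PQL σ_h | PQL σ_p | Power ML / PQL |
|---|---|---|---|---|---|---|---|
| 0.5 | 3 | 0.891 (2.44) | 0.820 (2.27) | 8% | 0.451 | 0.320 | 1.00 / 1.00 |
| 1 | 8 | 0.894 (2.44) | 0.787 (2.20) | 12% | 0.874 | 0.848 | 1.00 / 1.00 |
| 1 | 3 | 0.891 (2.44) | 0.725 (2.06) | 19% | 0.810 | 0.646 | 1.00 / 1.00 |
| 1 | 2 | 0.882 (2.42) | 0.693 (2.00) | 23% | 0.788 | 0.412 | 1.00 / 1.00 |
| 1.5 | 3 | 0.893 (2.44) | 0.640 (1.90) | 29% | 1.075 | 0.908 | 0.96 / 0.96 |
| 1.5 | 2 | 0.890 (2.44) | 0.601 (1.82) | 33% | 1.013 | 0.670 | 0.94 / 0.94 |

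Shortfall = 1 − PQL/0.895; for example, 1 − 0.601/0.895 = 0.33. The PQL person-level SD is 15% (1 − 0.848/1) to 59% (1 − 0.412/1) too small.

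A separate simulation used 204 households of 4 members, 3 swabs each, true log OR 0.90 and 100 replicates (Monte Carlo SE about 0.015). For (σ_h, σ_p) = (1, 1), (0.7, 1.5) and (1, 2), PQL-REML gave 0.73, 0.68 and 0.60. That is 19%, 25% and 34% too small, calculated before the means were rounded. Quadrature ML gave 0.90, 0.90 and 0.89. The PQL person-level SD was 36-41% too small.

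**6. REML or the linearisation?** A REML-type adjustment was applied to the quadrature likelihood in 24 replicates. With SDs of 1 and 3 measurements, log ORs were 0.887 (ML), 0.889 (ML with REML adjustment) and 0.723 (PQL-REML). With SDs of 1.5 and 2 measurements they were 0.900, 0.906 and 0.608. The linearisation causes the shrinkage.

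**7. Comparing fixed-effect sets.** The REML criterion contains log|XᵀV⁻¹X|, so multiplying one covariate by c shifts −2 log L by 2·ln c with an identical fit. In a simulated linear mixed model, the kind PQL fits to its working response:

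| Model | REML −2 log L | ML −2 log L |
|---|---|---|
| No age | 3169.72 | 3166.80 |
| Age in days | 3167.56 | 3149.96 |
| Age in months | 3160.73 | 3149.96 |
| Age in years | 3155.76 | 3149.96 |

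Months to years: 3160.73 − 3155.76 = 4.97 = 2·ln 12. The apparent gain from adding age is 2.16, 8.99 or 13.96 by REML, depending only on the unit. By ML it is 3166.80 − 3149.96 = 16.84 in every unit.

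**The case against.** - **REML is not the cause.** A reader might infer that REML as such shrinks the odds ratio. Step 6 shows that it does not. The bias needs PQL, which the document never names. It cites two papers for the method whose titles concern generalized and non-normal multilevel models, and what approximation they use cannot be seen here. This stands, so the bias must be stated as conditional on a pseudo-likelihood fit.
- **No ranking is planned.** A reader might infer that covariate models will be selected on invalid likelihoods. The section says only that such models will be built and associations surveyed; the only decision rule given is P < 0.05. This stands too: step 7 bites only if likelihoods are compared.
- **Power is not lost.** The test behaved alike under both fits. This stands, although four of the six scenarios were at 1.00 and only two could have shown a difference.
- **The simulations are simpler than the plan.** They have one family-type effect and random intercepts, with no time interaction, baseline term or random time effect. They keep all 102 households per group, whereas the Infected model section analyses only households with at least one ARI. The true effect is the widest pair from overlapping ranges. The percentages are therefore indicative.
- **Transmission is estimated elsewhere.** Acquisition and clearance rates come from the separate Bayesian susceptible-infected-susceptible model, so these variance components are not the study's only account of transmission. This is correct and limits the consequence.

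None of this makes the stated method adequate. As written it does not identify a fit for a two-state outcome, and its most common implementation is the biased one.

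**Conclusion.** The point holds in conditional form. The plan names an estimation method belonging to Gaussian mixed models for an apparently binary outcome and leaves distribution, link and integral approximation open. If run as restricted pseudo-likelihood, the family-type log odds ratio would be roughly 8% to 34% too small, for example an OR of 1.8 to 2.3 against a true 2.45, and the person-level and household-level SDs would also be too small. Quadrature ML recovered 2.42 to 2.44 in the main simulation.

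The direction was the same in every setting. The size rests on assumed SDs of 0.5 to 2 and 2 to 8 measurements per person, and is smallest with low variation or many swabs. The documents do not support saying that REML itself biases the estimate, that the test loses power, or that models will in fact be ranked on REML values. This should be corrected before analysis; it does not affect the design or sample size.

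**What to change.** In the HGLMEM section, replace the REML wording with a complete specification:

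- Infection status, separately for each pathogen, as a binomial outcome with logit link.
- Random effects for person and household, fitted by maximum likelihood with adaptive Gauss-Hermite quadrature, stating the software and number of points.
- A named fallback, Laplace or a Bayesian fit, if the three-level model with random time effects does not converge. Laplace was not tested in the simulations above, so if it is used, check it against quadrature in a random-intercept version of the model.
- If models with different fixed effects are to be compared, do so only on ML fits to the same observations, by likelihood ratio (nested models) or AIC.

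The cost is a few sentences of SAP wording and longer computing time. The real risk is non-convergence with unstructured random effects, because quadrature becomes heavy as random time effects are added; the fallback should therefore be fixed in advance. No change to data collection is needed.

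If a full-likelihood fit is already intended, the wording still needs changing, because naming REML alone does not convey it.

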If the households present with **respiratory symptoms**, the visit will be arranged as early as possible. When they presenting to the emergency department, outpatient clinic, or inpatient ward, the urine will be collected for the serotype-specific urinary antigen detection (SSUAD) assays in adult households and the nasopharyngeal or throat swab for PCR will be performed to study serotype of *S. pneumoniae* and RSV subgroup. If the subjects who have clinical syndromes suggestive of pneumonia or bronchopneumonia, they will be asked to participate in the further study along with their household family members. Nasopharyngeal aspiration, urine, blood, and induced sputum will be collected for cultures, PCR and serological test. Clinical manifestations, disease course, and outcomes will be recorded. Family members in the same household will be asked to undergo screening with a nasopharyngeal or throat swab and urine sample. We will trace back 2-week contact history of children in nuclear family who get RSV or pneumococcal infections, especially focus on other family members. The data will be further analyzed to evaluate the influence of short period and long period contact.

Case report form will be used to collect information about the family members, including demographic data, the number of bedrooms in the house, amount of contact time with the patient, presence and pattern of current or recent signs and symptoms and contact history with persons outside of the household who had clinical syndromes suggestive of *S. pneumoniae* or RSV infection.

Follow-up telephone interviews repeated questions about signs and symptoms at 2, 4, and 8 weeks. If any household family member reported experiencing signs or symptoms suggesting *S. pneumoniae* or RSV infection during the follow-up period, clinical assessment and laboratory investigation will be repeated.

	Data collection	Specimen collection
Enrollment	1. information consent form 2. baseline data, including patient demographics, prior medical history, season when discharge, neonatal course and households	
Line follow up period	Checking if there are any respiratory symptoms	
Index case presents symptoms suggesting upper respiratory tract infection		Index case 1. Serotype-specific urinary antigen detection (SSUAD) assays 2. Nasopharyngeal or throat swab for PCR will be performed to study serotype of S. pneumoniae and RSV subgroup. RSV will be sequenced to ascertain F protein heterogeneity.

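### Categorical tests, including by inference those on serotype, have no stated unit of analysis and no allowance for household clustering, so comparisons between family types at isolate level would give p-values that are too small

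*Combined protocol and SAP*

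**What the plan says.** The Study endpoint section sets the primary endpoint as *S. pneumoniae* and RSV "isolation rates in children and their household contacts of different family type". It then says "The secondary endpoint is the serotype of" *S. pneumoniae* and RSV in the post-PCV13 era. No comparison, hypothesis or test is attached to the secondary endpoint.

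The last paragraph of the HGLMEM part of Statistical Methods gives the general rule: "Categorical variables will be presented as frequency and percentage and compared using chi-square or" Fisher's exact test, whichever is appropriate, with P below 0.05 counted as significant. Continuous variables go to the Mann-Whitney test. Neither sentence names a unit of analysis.

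The same section plans a three-level model (time points within subject within household). Its outcome is always *S. pneumoniae* or RSV "infection status across time points and to survey the potential associations between these outcomes and independent variables". Serotype, RSV subgroup and antimicrobial nonsusceptibility are not named as outcomes.

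On sampling, Study design says that when a participant has suspected pneumonia or bronchopneumonia, "Family members in the same household will be asked to undergo screening with a nasopharyngeal or throat swab and urine sample". If a household member reports suggestive symptoms during follow-up (interviews at 2, 4 and 8 weeks), "clinical assessment and laboratory investigation will be repeated". The Infected model part of Statistical Methods adds that a household with ARI in different years is treated as two households.

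**The concern.** A chi-square or Fisher test assumes that each counted item is independent. Here one household can contribute several serotyped detections, from different members or from one person at successive investigations. The study is designed around the premise that these people pass strains to one another. A single transmitted strain could then be counted several times as separate evidence.

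Family type is a property of the household, so a comparison between family types sets whole clusters against whole clusters. Ignoring the clustering there understates the variance, and a difference in serotype distribution could reach P<0.05 with no true difference behind it. If the rule that splits households by year were carried over to these comparisons, even a household-level test would count some families twice.

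The plan already recognises person and household as levels for infection status. The gap is that nothing comparable is specified for the other categorical outcomes.

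**Working it through.** **No figure of the plan's own to reproduce.** The plan gives no calculation for serotype comparisons. Its sample size of 93 per group concerns the incidence of household-acquired *S. pneumoniae* and does not bear on this point.

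**Inputs.** From the plan: the test (chi-square) and the threshold (0.05). Assumed, because the documents give none of them: 60 positive households per group; 10 equally common serotypes; *m* serotyped isolates per positive household; each isolate after the first copies the first isolate's strain with probability *c* = 0.3 to 0.6 and is otherwise drawn at random.

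**Design effect.** Under this model, the correlation between the first isolate and a later one is *c*, and between two later ones it is *c*². Hence

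DE = 1 + 2[(*m*−1)*c* + ((*m*−1)(*m*−2)/2)*c*²]/*m*.

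For a mix of 70% of households with one isolate, 20% with two and 10% with three, the mean is 0.7 + 0.4 + 0.3 = 1.4, and

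DE = 1 + [0.2(2*c*) + 0.1 × 2(2*c* + *c*²)]/1.4.

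**False-positive rate between family types.** Ten serotypes in two groups give 9 degrees of freedom and a 5% critical value of 16.92. The true rate is about P(χ²₉ > 16.92/DE). Example: *m* = 2, *c* = 0.3 gives DE = 1.3, 16.92/1.3 = 13.01, and a rate of 16%.

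| Isolates per positive household | DE (*c* = 0.3; 0.6) | Formula | Simulation |
|---|---|---|---|
| 1 | 1; 1 | 5% | 4-5% |
| mix, mean 1.4 | 1.18; 1.39 | 11%; 21% | 10-11%; 19-20% |
| 2 | 1.30; 1.60 | 16%; 31% | 16-18%; 30-32% |
| 3 | 1.46; 2.04 | 24%; 51% | 24-25%; 50-52% |
| 4 | 1.59; 2.44 | 30%; 64% | 29-31%; 64-65% |

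Simulation ranges cover repeated runs of 3,000 to 4,000 replicates or similar. The one-isolate row is the control, and it behaves correctly.

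**Two-category variables.** With 1 degree of freedom, the same DE values of 1.3 and 1.6 at *m* = 2 give only 9% and 12%. A general form, DE = 1 + (*m*−1)ICC with an assumed ICC of 0.1 to 0.8, gives 6-14% for *m* = 2 and 9-29% for *m* = 4. Inflation grows with the number of categories, which is why serotype is more exposed than, say, RSV A versus B.

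**Age groups within the same households.** Here a shared strain makes the two groups more alike. With the ten-serotype set-up, the false-positive rate is about 0-1% for both 2 and 4 isolates per household. In the two-category version it is about 2% at ICC 0.3. These p-values are too large.

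**The case against.** The strongest reply is that the plan never says serotype will be tested at isolate level. The categorical rule is generic, it follows a sentence about descriptive summaries, and the secondary endpoint has no stated comparison. Serotype might only be described. That stands: the defect is an unspecified unit, not a specified wrong one. But the plan supplies no other test for these outcomes, so applying it as written leads to the plain test.

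Second, isolates per household may be few. Family swabbing is tied to suspected lower respiratory infection, not to every upper respiratory episode, and only positive samples yield a serotype. This also stands, and it is why the low end matters. With the 70/20/10 mix and only 20 positive households per group, the rate is 7-15%, which is smaller but still above 5%.

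Third, a reader might infer that all p-values for the secondary endpoint are far too small, including those by age. The documents do not support that. Comparisons between members of the same households become conservative. Children versus elderly is partly of this kind, although by definition grandparents occur only in extended families, so a comparison pooled over both types would be mixed.

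Fourth, a reader might extend the concern to positivity by family type. That is infection status, which the three-level model covers. Nor do the documents show that a few clustered households would drive the serotype shares.

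Finally, counting one isolate per household and episode changes the quantity from carriage among persons to strains per household. That is fair, so such a count belongs in a sensitivity analysis.

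**Conclusion.** The concern holds in limited form. For categorical outcomes other than infection status, the plan states no unit of analysis and no allowance for household or repeat-isolate clustering, although its sampling produces both. Isolate-level comparisons between family types would be anti-conservative: roughly 10-32% false positives at a nominal 5% for a ten-category serotype test with 1.4 to 2 isolates per positive household, and about 24-65% with 3 or 4. Two-category variables are affected less.

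These sizes rest on the assumed number of positive households, equally common serotypes, isolates per household and copying rate. The direction between family types does not depend on the exact values, provided that some households yield more than one isolate and strains are shared. That serotype would be tested this way is an inference, though the likeliest one. The point should be fixed, but it concerns a secondary endpoint without a stated hypothesis and leaves the planned infection-status model untouched.

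**What to change.** In Statistical Methods:

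- State the unit of analysis for each categorical outcome, and whether each is compared or only described.
- For comparisons of serotype, RSV subgroup and nonsusceptibility, obtain p-values and confidence intervals clustered on the enrolled household: household bootstrap or permutation, a Rao-Scott test, or GEE. This corrects the error in both directions.
- Keep the same enrolled household as one cluster across years in these analyses, whatever the transmission model does.
- Report serotype percentages also with one isolate per serotype per household per episode, as a sensitivity analysis.
- Keep plain chi-square, Fisher and Mann-Whitney tests for variables with one value per household.

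This needs wording and code but no new data. The cost is slightly more analysis work and wider intervals for comparisons between family types.
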